The primary behavioral outcome measure of treatment success will be the count of unprotected anal sex acts and the biomedical endpoint will be NG/CT incidence (Aim 2). Secondary outcomes include: condom errors, IMB factors, and receipt of an HIV test. We will also explore intervention effects separately for receptive and insertive anal sex. The primary independent variable of interest is the indicator for the intervention group. The baseline value of the outcome and other required covariates at baseline will be included as additional independent variables. The intervention will recruit participants from multiple sites (multiple clinics in three cities); however it is not delivered in groups so site will be adjusted for as a fixed rather than a random independent variable. A random intercept term will be included to account for individual average levels of the outcome. The effect of time will first be estimated as a categorical variable in order to describe and adjust for time trends as observed. A second strategy will start with estimating a single slope reflecting average change across all 4 time points, then add a guadratic term if it contributes significantly to the model. Random effects for time variables, reflecting individual variations in time trends, will be included in addition to random intercepts, if significant. A single effect of group will test the intervention effect averaged across all time points, adjusting for all included covariates and underlying time trends. Potential moderators (race/ethnicity, relationships status, and gay/bisexual identity) will be added as independent variables and their interactions with intervention group will be tested (Aim 3). Addition of interaction terms between time and intervention group will provide a test for comparing time trends in change scores between groups.

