Analysis of all available measurements among all participants regardless of dose is consistent with an "intent-totreat" perspective¹⁷². It is desirable to also perform an analysis which considers the "dose" and engagement in the intervention. We will use Rubin's causal modeling to consider dose-effect when making comparisons across the two groups^{208,209}. Further, in our HLM models, missing data is assumed to be missing at random conditional on the independent variables in the model; therefore we are in effect assuming that participants with incomplete measurements would have been similar to others in their group (their same covariate values) with complete measurements.

D. Quality Assurance

D.1. Procedures in place to ensure the validity and integrity of the data.

All project staff (from investigators to research associates) have extensive experience interacting with our research populations in a sensitive and understanding manner so as to increase the comfort of research participants and ensure comprehensive and valid data collection. In addition, all have completed the required on-line training for the protection of human subjects. Our use of self-administered electronic systems for collecting data will also serve to enhance the reliability and validity of the data from each participant. Private self-report increases the proportion of individuals admitting sexual behaviors and illicit drug use. As such, these measurement modalities allow for greater respondent privacy and remove barriers to honest responding, such as embarrassment, feedback from interviewer facial expressions, and other social influences.

D.2. Procedures in place to ensure the accuracy and completeness of the data.

D.2.a. Health Information Technology protocols. Given the online nature of this study, our HIT team will include professional quality assurance staff who will provide software testing and troubleshooting for new and existing HIT systems, including development of test plans, test cases and test scripts. The HIT team will ensure that the intervention functionality operates properly and that the content is accurate, complete and clear.

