H1. Responsibility for Data and Safety Monitoring.

The overall responsibility for data and safety monitoring lies with [name]. As PI, he is responsible for the accurate documentation, investigation and follow-up of all possible study-related adverse events. Any unexpected or SAEs that occur during the course of the study will be reported by the PI to the NU IRB in accordance with current University guidelines for reporting adverse events. The PI will regularly review all data related to adverse events. The PI, Co-Is, and study staff will teleconference on a monthly basis to discuss enrollment, retention, and safety of study participants.

H2. Frequency of DSM.

Information related to recruitment, enrollment, and retention will be relayed to the DSMB every six months, unless the Board requests otherwise.

H3. Content of DSM report.

The project staff will prepare an annual report which will include: (1) a brief description of the trial; (2) baseline sociodemographic characteristics; (3) retention and disposition of study participants; (4) QA issues; (5) regulatory issues; (6) AEs; (7); SAEs; and (8) efficacy.

I. DSMB Plan

In accordance with the National Institutes' of Health requirement that multisite clinical trials have Data and Safety Monitoring Boards (DSMB), we will establish a DSMB according to policies and requirements put forth by NIH. Specifically: (1) the DSMB must include a minimum of 3 individuals; (2) board members must have no direct involvement with the intervention or study and no other conflict of interest with the intervention or study; (3) the board must meet at least two times per year during periods when intervention and/or data collection are taking place and at least once per year during other phases (e.g., developmental phase or analysis phases).

[name], the PI, has served on numerous DSMBs for HIV prevention trials and is familiar with their organization and operation. The Northwestern University Clinical and Translational Sciences Institute (NUCATS) will assist in establishing protocols for managing the DSMB. The proposed study is considered to present minimal risk to participants given that subjects will complete questionnaires, receive STI tests, and participate in a behavioral intervention.

I.1. Members and affiliations.

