The DSMB will conduct an open session prior to the initiation of the trial. The DSMB will have been provided with all material associated with the trial, and have had sufficient opportunity to review the documents. At the open session all members will discuss any potential concerns for the safe and effective conduct of the impending study. With data collection beginning in Year 1, DSMB meetings will be held every 6 months. However, the Chair of the DSMB can call a meeting as needed. Serious adverse events will be reported to the Chair as soon as they occur. The Chair of the DSMB will determine whether an in-person meeting or teleconference is needed. Prior to the meetings, a written report containing any outcome data will be sent to DSMB members by the study statistician. Each meeting will be divided into three parts. (1) There will be an open session in which the PI will be present to review the progress of the study and to answer questions from members of the DSMB. (2) A closed session involving the DSMB members and the study statistician will be held during which outcome results will be discussed. (3) A final session involving only the DSMB members will be held to discuss the progress of the study and the outcome results, to develop recommendations, and to takes votes as necessary.

I.3. Conflicts of interest.

Members of the DSMB will disclose any potential conflicts of interest, either pre-existing or those that develop during their tenure, to the PI and the NIDA PO.

I.4. Protection of confidentiality.

Member of the DSMB will protect the confidentiality of the trial data and the monitoring results.

I.4. Monitoring activities.

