I.4.a. Members of the DSMB will perform the following activities: (1) review the research protocol and plans for data and safety monitoring; (2) review progress of the trial, including analysis of data quality and timeliness; subject recruitment, randomization and retention; subject risk versus benefit; and other factors that may affect outcome; (3) review SAE reports, provide commentary, and provide oversight to ensure that reports are relayed to individual IRBs and to the Office of Human Research Protections, as indicated; (4) review analyses of outcome data of the proposed study and review reports of related studies; (5) determine whether the trial should continue as designed, should be changed, or should be terminated based on the data and make recommendations to the NIH, Institutional Review Boards, and investigators considering conclusion or continuation of the study; (6) review proposed modifications to the study prior to their implementation; (7) protect the confidentiality of the trial data and the results of the monitoring; (8) determine whether and to whom outcome results should be released prior to the reporting of study results; (9) following DSMB meetings, provide appropriate NIH staff and the PI with written information concerning their findings.

I.4.b. The PI, [name], will be responsible for the following: (1) preparation and establishment of a plan for the data and safety monitoring; (2) evaluation of all members of the DSMB for a conflict of interest or financial stake in the outcome of the trial; (3) delegation of the ongoing monitoring of the trial to the DSMB; (4) ensuring that monitoring is timely and effective and that the DSMB is composed of individuals with appropriate expertise to accomplish their assigned tasks; (5) overseeing the monitoring activities; (6) responding to and addressing recommendations that result from monitoring activities; (7) provision of adverse event reports and other safety data to the DSMB, as well as any changes in the trial or annual reports to the IRB and NIDA; (8) contributing to the report that the DSMB generates, which will be distributed to the IRB and NIDA; (9) submitting the DSMB report to the IRB.

I.5. Communication plan to IRB and NIDA.

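### SAP H3 puts efficacy in a yearly report written by project staff, which conflicts with the plan's own closed route for interim outcome results

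*SAP*

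**What the plan says.** SAP H3 sets the content and authorship of the monitoring report: "The project staff will prepare an annual report which will include: (1) a brief description of the trial". The list closes with "6) AEs; (7); SAEs; and (8) efficacy". H3 does not separate an open from a closed part, name a different author for the efficacy item, or say whether efficacy is pooled or split by arm.

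The meetings paragraph of SAP section I (DSMB Plan) says that before each meeting "a written report containing any outcome data will be sent to DSMB members by the study statistician". It then divides the meeting. For the investigator: "There will be an open session in which the PI will be present to review the progress of the study". For results: "A closed session involving the DSMB members and the study statistician will be held during which outcome results will be discussed". A last session is for board members alone. SAP I.4.a lists among the board's tasks to "determine whether and to whom outcome results should be released prior to the reporting of study results".

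On modeling, Protocol B.11 and SAP C3 add as covariates any variables that differ significantly between arms at baseline, add a quadratic time term if it is significant, and say that random effects for time "will be included in addition to random intercepts, if significant".

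**The concern.** A closed session exists so that the people who run a trial do not learn the running treatment effect. H3 gives those people a document to write that contains it. If H3 is followed, the board's power to decide who sees results early is pre-empted, because the authors of the report have already seen them.

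What is at stake is the credibility of the primary comparison. The primary behavioral outcome is a self-reported count of acts. Retention is worked by staff, and the mixed models assume data missing at random (Protocol B.11, SAP C3). Staff who know the trend could, without intending to, press harder for some follow-up than for other follow-up, or change how they support participants. The missing-at-random assumption would not repair effort that varies by arm for reasons outside the model.

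**Working it through.** No power, error-rate or sample-size figure is involved, so the check is a comparison of the text.

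1. **The two routes side by side.**

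| Question | SAP H3 | SAP section I |
|---|---|---|
| Who writes the efficacy material? | Project staff | Study statistician |
| Who receives it? | Not stated | DSMB members |
| Is there a closed part? | None | Yes: board and statistician only |
| Who controls early release? | Not addressed | The DSMB (I.4.a) |

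2. **Who are project staff?** The SAP uses the term broadly. Section D.1 begins: "All project staff (from investigators to research associates) have extensive experience interacting with our research populations". Section F.3.e.(i) also uses it for people in personal contact with participants. It is not a label for a separate statistical unit.

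3. **Would efficacy be by arm?** H3 does not say so. The trial has two arms, and SAP G.1, under the heading Trial Efficacy, has the board look for harm in either condition. A comparison of arms is therefore the natural reading, but it is an inference.

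4. **Does other text close the gap?** Section F.3.e.(i) keeps tracking staff away from survey data, to stop identities being linked to answers. That covers individual records, not aggregate results, and it does not cover investigators or coordinators. The confidentiality duty for monitoring results in section I is placed on board members; no matching duty is stated for staff.

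5. **Where could knowledge act?** Protocol B.10(b3) lets the coordinator decide on further calls about unreturned STI kits once the scheduled reminders are used up, and B.10(b1) sets no limit on contact attempts during the study. Protocol C.1.a raises the 12-month payment from \$30 to \$50 for participants who are hard to reach and out of window. Effort that differs by arm would also require the coordinator to know the participant's arm; I found no statement in either document on whether coordinators are masked.

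6. **How often?** Protocol B.10 places the trial in months 7 to 54: 54 − 7 + 1 = 48 months, and 48 / 12 = 4 yearly reports. Protocol C.1.a gives months 7 to 48: 48 − 7 + 1 = 42 months, and 42 / 12 = 3.5. So there would be about three or four reports, the earliest with little follow-up data. This counts occasions; it does not measure bias.

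7. **The separate modeling point.** Under section I the study statistician sees outcome results at meetings held every six months, whatever H3 says. Covariates, the quadratic term and the random time effects are meanwhile left to be chosen from the data. Removing efficacy from H3 would not change this, so it needs its own remedy.

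**The case against.** The best defense is that H3 and section I can be read together. H3 lists what the monitoring report contains; section I says who supplies outcome data and who discusses it. The statistician may count as project staff, may write the efficacy item alone, and may send it only to the board. This is possible, but it is not written, and D.1 points to the wider meaning of the term. The defense shows that the conflict may be harmless in practice; it does not remove it from the text.

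Several limiting facts stand. Allocation and content delivery are automated online, and many reminders follow a fixed schedule. The other primary outcome is a laboratory result on kits identified by study number. Staff log individual STI results in any case (SAP F.3.e.(vii)), so what needs protecting is the aggregate comparison of arms.

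A reader might infer more than the documents support:

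- *That staff have seen results by arm.* Nothing shows that a report with such content was written or circulated.
- *That about 20% of follow-up hangs on staff effort.* The only related figure is the 80% retention assumed in Protocol B.12. Its complement, 100% − 80% = 20%, is expected loss.
- *That staff book late 12-month visits.* Assessments are online and kits are normally mailed; C.1.a describes only a higher payment for late completion.
- *That H3 is what exposes the statistician.* The closed-session route does that by itself, and the documents do not say that this statistician makes the model choices or runs the final analysis.

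**Conclusion.** The conflict is real and stands on the face of the SAP: one section has staff write up efficacy, while another keeps outcome results with the statistician and the board. Its consequence is a risk of operational bias that is neither demonstrated nor quantifiable from these documents. The risk rests on three assumptions: that H3 is followed literally, that its efficacy item is split by arm, and that the authors include people who manage participants. For retention that differs by arm, it also requires staff to know allocation. The point should be corrected because the rule works against the plan's own safeguard and the correction is nearly free. It does not by itself invalidate the trial.

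The data-dependent model terms are a secondary pre-specification issue and should be judged separately. Asking for sign-off before the first closed report is probably no longer possible. The SAP is dated November 2016, refers in A.3 to 900 participants already enrolled, and has the board meeting every six months once data collection begins in Year 1.

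**What to change.** 1. In SAP H3, delete the efficacy item from the report that project staff prepare, or limit it to outcome data pooled across arms. Add a sentence that efficacy by arm appears only in the study statistician's closed report to the DSMB, with early release decided by the board under I.4.a.

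2. Record whether any yearly report has already carried efficacy, in what form, and who saw it.

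3. Separately, fix and date the primary model now, before any further outcome results by arm are reviewed: distribution, covariates, coding of time, and random effects. Attach a record of which outcome results have been seen, when and by whom.

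Cost: one line in H3, a short file note, and a dated statement of the model. No extra staff, participants or data are needed.

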The DSMB will conduct an open session prior to the initiation of the trial. The DSMB will have been provided with all material associated with the trial, and have had sufficient opportunity to review the documents. At the open session all members will discuss any potential concerns for the safe and effective conduct of the impending study. With data collection beginning in Year 1, DSMB meetings will be held every 6 months. However, the Chair of the DSMB can call a meeting as needed. Serious adverse events will be reported to the Chair as soon as they occur. The Chair of the DSMB will determine whether an in-person meeting or teleconference is needed. Prior to the meetings, a written report containing any outcome data will be sent to DSMB members by the study statistician. Each meeting will be divided into three parts. (1) There will be an open session in which the PI will be present to review the progress of the study and to answer questions from members of the DSMB. (2) A closed session involving the DSMB members and the study statistician will be held during which outcome results will be discussed. (3) A final session involving only the DSMB members will be held to discuss the progress of the study and the outcome results, to develop recommendations, and to takes votes as necessary.

I.3. Conflicts of interest.

Members of the DSMB will disclose any potential conflicts of interest, either pre-existing or those that develop during their tenure, to the PI and the NIDA PO.

I.4. Protection of confidentiality.

Member of the DSMB will protect the confidentiality of the trial data and the monitoring results.

I.4. Monitoring activities.

I.4.a. Members of the DSMB will perform the following activities: (1) review the research protocol and plans for data and safety monitoring; (2) review progress of the trial, including analysis of data quality and timeliness; subject recruitment, randomization and retention; subject risk versus benefit; and other factors that may affect outcome; (3) review SAE reports, provide commentary, and provide oversight to ensure that reports are relayed to individual IRBs and to the Office of Human Research Protections, as indicated; (4) review analyses of outcome data of the proposed study and review reports of related studies; (5) determine whether the trial should continue as designed, should be changed, or should be terminated based on the data and make recommendations to the NIH, Institutional Review Boards, and investigators considering conclusion or continuation of the study; (6) review proposed modifications to the study prior to their implementation; (7) protect the confidentiality of the trial data and the results of the monitoring; (8) determine whether and to whom outcome results should be released prior to the reporting of study results; (9) following DSMB meetings, provide appropriate NIH staff and the PI with written information concerning their findings.

I.4.b. The PI, [name], will be responsible for the following: (1) preparation and establishment of a plan for the data and safety monitoring; (2) evaluation of all members of the DSMB for a conflict of interest or financial stake in the outcome of the trial; (3) delegation of the ongoing monitoring of the trial to the DSMB; (4) ensuring that monitoring is timely and effective and that the DSMB is composed of individuals with appropriate expertise to accomplish their assigned tasks; (5) overseeing the monitoring activities; (6) responding to and addressing recommendations that result from monitoring activities; (7) provision of adverse event reports and other safety data to the DSMB, as well as any changes in the trial or annual reports to the IRB and NIDA; (8) contributing to the report that the DSMB generates, which will be distributed to the IRB and NIDA; (9) submitting the DSMB report to the IRB.

I.5. Communication plan to IRB and NIDA.

[name] will promptly inform NIDA and the IRB of any changes in recruitment or in the protocol relevant to safety as the study is being performed. He will additionally notify NIDA of any actions taken by the IRB during continuing study review and of any major changes in the status of the ongoing protocol which would only occur with IRB approval. Such changes would include, but are not limited to: (1) amendments to the protocol; (2) temporary suspension of patient accrual, or of the protocol; (3) changes in informed consent or

IRB approval status; (4) termination of participant accrual or of the protocol; or (5) other problems or issues that could affect the human subjects in the study.
